6.2.3 Rescue medication

Not Applicable

6.2.4 Other Concomitant medications

Anti-emetics

Use of anti-emetics is allowed. Prophylactic anti-emetics should be started only once the patient experiences nausea or vomiting, at the discretion of the investigator. It is recommended that patients use drugs that do not cause QT prolongation. Please note that some anti-emetics have a known risk for Torsade de Pointes and are prohibited (refer to [Section 6.2.1.1](#) and [Section 16 Appendix 1](#)).

Contraceptives

Hormonal contraceptives are allowed as contraception methods. Highly effective contraception should be maintained throughout the study and for 7 days after study treatment discontinuation.

Anticoagulation agents

All anticoagulants or anti-aggregation agents may be administered under the discretion of the investigator.

Therapeutic doses of warfarin sodium (Coumadin®) or any other coumadin-derivative anticoagulants should be used with caution and fully avoided whenever possible because of its known interaction with many commonly used medications and certain foods. As warfarin has a narrow therapeutic range, and asciminib is a weak inhibitor of CYP2C9, the major metabolizing enzyme of S-warfarin (R-warfarin is metabolized by multiple CYP enzymes), warfarin should be carefully monitored whenever used.

Caution is also advised when asciminib is co-administered with anti-platelet pro-drugs such as clopidogrel, ticlopidine and prasugrel, which require metabolic activation by CYP3A4 and CYP2C9. While the weak reversible *in vitro* inhibition potential of asciminib is unlikely to translate into clinical significance as the steady-state plasma concentrations at the maximum therapeutic doses are significantly lower than the experimentally determined inhibition constants, patients using anti-platelet pro-drugs should still be carefully monitored.

Direct Thrombin inhibitors (DTIs) and Factor Xa inhibitors are allowed as anticoagulants. Individual medications from each of the classes should be checked if they are not prohibited due to other drug-drug-interactions with asciminib. Alternatively, therapeutic anticoagulation may be accomplished using low-molecular weight heparin.

6.3 Participant numbering, treatment assignment, randomization

6.3.1 Participant numbering

Each participant is identified in the study by a Participant Number (Participant No.), that is assigned when the participant is enrolled for screening and is retained for the participant throughout his/her participation in the trial. A new Participant No. will be assigned at every subsequent enrollment if the participant is re-screened. The Participant No. consists of the Center Number (Center No.) (as assigned by Novartis to the investigative site) with a sequential participant number suffixed to it, so that each participant's participation is numbered uniquely across the entire database. Upon signing the informed consent form, the participant is assigned to the next sequential Participant No. available.

A new ICF will need to be signed if the investigator chooses to re-screen the participant after a participant has screen failed, and the participant will be assigned a new Participant No.

6.3.2 Treatment assignment

For all CML-CP, with the exception of those harboring the T315I mutation, patients will be randomly selected to minimize selection bias at the time of cohort allocation. Those patients will be assigned to either Cohort A consisting of asciminib 40 mg BID patients or Cohort B consisting of asciminib 80 mg QD. For CML-CP patients harboring the T315I mutation, they will be assigned to Cohort C with asciminib 200 mg BID, which is the dose required for that patient population. Random selection for cohorts A and B will be for the sole purpose of patient selection. The study is not powered to show differences in Primary and Secondary endpoints.

6.4 Treatment blinding

Not Applicable

6.5 Dose escalation and dose modification

Investigational or other study treatment dose adjustments and/or interruptions are not permitted.

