4.4 Risks and benefits

Appropriate eligibility criteria, as well as specific dose modification and stopping rules in the event of expected toxicities, are included in this protocol. Recommended guidelines for prophylactic or supportive treatment for expected toxicities, including management of study-drug induced adverse events are provided in Section 6.5.4. Patients who have failed 2 prior TKIs are at increased risk of progression to more advanced phases of CML such as CML-AP and CML-BC. Currently available therapeutic agents in this setting are non-curative and patients remain at risk of progressing after short duration of remissions ([Khoury 2012](#)).

An important potential risk for patients enrolling on the 80 mg QD arm is the possibility of having either higher toxicity or reduced efficacy. However, as mentioned above, the evidence to date of such dose on a similar population of patients in the study [[CABL001X2101](#)] suggests that asciminib is an active and safe agent. Further, the adverse event profile of asciminib is similar qualitatively to that observed with other TKIs targeting BCR-ABL1 (Section 1.1.2.2). The risk of 80 mg QD of asciminib not being effective has been mitigated in that patients will be observed closely for evidence of efficacy, based on assessment of hematologic and molecular response data, which will permit rapid decision making as to discontinuation of therapy if necessary.

Another relevant risk is the potential for higher rates of toxicity in patients harboring the T315I mutation, who will be receiving the dose of 200 mg BID. As previously mentioned, our [[CABL001X2101](#)] study where more than 50 patients with that mutation were treated with that dose showed encouraging safety data and so, it is fairly unlikely that more AEs will be occurring in this patient population.

Other risks to subjects in this trial will be minimized by compliance with the eligibility criteria and study procedures, close clinical monitoring, and adherence to dose modification and interruption guidance provided in the protocol.

The currently available information suggests that there is equivalence between the two arms with respect to benefit / risk to enable inclusion of patients in this study.

There may be unforeseen risks with asciminib which could be serious. Refer to the latest [[Asciminib Investigator's Brochure](#)] for additional details.

5 Study Population

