6.2.2 Prohibited medication

Other anticancer agents

The administration of any other anticancer agents including chemotherapy and biologic agents is not permitted except for anti-cancer treatments of newly diagnosed solid cancers (e.g. prostate cancer) that would not impact the level of minimal residual disease of patients. These patients may remain in the current study after consultation with Novartis. The administration of other tyrosine kinase inhibitors indicated for treatment of CML are **not** allowed.

Strong CYP3A inducers

Any strong CYP3A inducers should be discontinued 7 days before the first dose of study medications.

Every effort should be made NOT to concomitantly administer strong CYP3A inducers during the study. If administration of a strong CYP3A inducer cannot be avoided during the study and cannot be switched to an alternative therapy, investigator should exercise caution while patient is on study treatment.

Cohort C only (200 mg BID): Strong CYP3A inhibitors

Any strong CYP3A inhibitors should be discontinued 7 days before the first dose of study medications.

Every effort should be made NOT to concomitantly administer strong CYP3A inhibitors. CYP3A inhibitors may decrease the metabolism of asciminib and resulting in increased plasma concentrations and increased exposure. If administration of a strong CYP3A inhibitor cannot be avoided during the study and cannot be switched to an alternative therapy that does not strongly inhibit CYP3A, asciminib must be interrupted.

A list of cytochrome P450 isoenzymes and CYP3A inhibitors may be found at medicine.iupui.edu/CLINPHARM/ddis/clinical-table.

A classification of CYP3A SmPC can be found in Section 16, [Table 16-2](#).

Further information can also be found in the following reference ([Venkatakrishnan et al 2001](#)).

UGT1A/2B inducers

The use of strong inducers of UGT1A/2B is prohibited during the study.

If administration of UGT1A/2B inducer cannot be avoided during the study and cannot be switched to an alternative therapy, temporary interruption of study treatment is NOT needed.

QT prolonging agents

As far as possible avoid co-administering drugs with a “Known”, “Possible” or “Conditional” risk of Torsades de Pointes (per www.crediblemeds.org/) during the course of the study:

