- If concomitant administration of drugs with a “Known risk of Torsades de Pointes” is required and cannot be avoided, study drug must be interrupted. If, based on the investigator assessment and clinical need, study treatment is resumed, close ECG monitoring is advised.
- If during the course of the study, concomitant administration of a drug with “Possible risk” or “Conditional risk of Torsades de Pointes” is required, based on the investigator assessment and clinical need, study treatment may be continued under close ECG monitoring to ensure patient safety.

A list of drugs associated with QT prolongation and/or Torsades de Pointes is available online at www.crediblemeds.org/.

Herbal medications

Herbal preparations/medications are not allowed throughout the study. These herbal medications include, but are not limited to: St. John’s wort, Kava, ephedra (ma huang), ginkgo biloba, dehydroepiandrosterone (DHEA), yohimbe, saw palmetto, and ginseng. Patients should stop using these herbal medications 7 days prior to first dose of study drug.

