6.5.2 Dose modifications

For patients who do not tolerate the protocol-specified dosing schedule, dose interruptions and/or reductions are either recommended or mandated in order to allow the patient to continue the study treatment.

These dose modifications are summarized in [Table 6-2](#). The dose reduction indicated as “recommendations” is provided to assist investigators in the event the patient experiences toxicity. However, deviations from “mandatory” dose interruptions and/or reductions are not allowed and mandatory interruptions or reductions must be strictly followed. Re-escalation to asciminib 40 mg BID is permitted if a change in the patient’s individual benefit/risk assessment at the lower dose level is seen. Re-escalation will be allowed only once for any given patient. Permanent treatment discontinuation is mandatory for specific events indicated as such in [Table 6-2](#). Any dose changes must be recorded on the Dosage Administration Record eCRF.

A patient must discontinue treatment with Asciminib if, after treatment is resumed at a lower dose level, the toxicity recurs with the same or worse severity, except for recurrence of cytopenias ([Table 6-2](#)). If a patient requires a dose interruption of > 28 days for each non-hematologic toxicity, then the patient must be discontinued from the study treatment. If a hematologic toxicity (cytopenia Grade 3 or 4) lasts for more than 42 days without recovery to at least a Grade 2, despite TKI interruption and adequate management (including hematopoietic growth factors), then the patient must be discontinued from the study treatment.

These dose changes must be recorded on the appropriate case report form (CRF).

Table 6-2 Criteria for dose reduction / interruption and re-initiation of asciminib treatment for adverse drug reactions.

| Dose modifications for asciminib | |
|---|--|
| Please note that if a patient requires a dose interruption of > 28 days for each toxicity, then the patient must be discontinued from the study treatment | |
| Worst toxicity CTCAE Grade 5 | Asciminib |
| Investigations (Hematologic) If a hematologic toxicity (cytopenia Grade 3 or 4) lasts for more than 42 days without recovery to at least a Grade 2, despite TKI interruption and adequate management (including hematopoietic growth factors), then the patient must be discontinued from the study treatment. | |
| Neutropenia (ANC) | |
| Grade 1 (ANC < LLN – 1.5 x 10 ⁹ /L) | Recommendation: Maintain dose level |

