6.5.2.1 Dose adjustments for QTcF prolongation

If QTcF >500 msec or QTcF prolongation >60 msec from baseline is observed at any point during study treatment, and confirmed, the below guidance must be followed:

1. Assess the quality of the ECG recording and the QT value and repeat if needed
2. Interrupt study treatment until confirmed resolution of QTcF and as per dose reduction guidelines for non-hematological AEs.
3. Determine the serum electrolyte levels (in particular hypokalemia and hypomagnesemia). If abnormal, correct abnormalities before resuming study treatment.
4. Review concomitant medication associated with QT prolongation, including drugs with a “Known”, “Possible”, or “Conditional risk of Torsades de Pointes” (refer to www.crediblemeds.org/), and drugs with the potential to increase the risk of study drug exposure related QT prolongation.
5. Check the dosing schedule and treatment compliance

After confirming ECG reading at site, if QTcF > 500 msec

- Interrupt study treatment
- Repeat ECG and confirm ECG diagnosis by a cardiologist or central ECG lab
- If QTcF confirmed > 500 msec:
 - Correct electrolytes, eliminate culprit concomitant treatments, and identify clinical conditions that could potentially prolong the QT as per the ECG and QTc Clinical Safety Standards Guidelines
 - Consult with a cardiologist (or qualified specialist)
 - Increase cardiac monitoring as indicated, until the QTcF returns to ≤ 480 msec
- After resolution to ≤ 480 msec, consider re-introducing treatment at reduced dose, and increase ECG monitoring (e.g., pre dose and 2 hours post dose after one week and two weeks of treatment re-introduction)
- If QTcF remains ≤ 500 msec after dose reduction, continue planned ECG monitoring during subsequent treatment
- If QTcF recurs > 500 msec after dose reduction, discontinue subject from trial

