6.6.3 Special Considerations for COVID-19 infection

All patients that who present with COVID-19 infection or who become COVID-19 positive on treatment should be placed immediately on treatment break or delay while a determination is made about the next steps

A request to start or continue treatment of COVID-19 positive patients should be considered in the context of medical necessity to start or continue treatment with the study drug.

Many patients with previous COVID-19 infection may be appropriate to be considered eligible for inclusion in the study if tested negative after initial infection

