8.1.3 Treatment Period

All patients will be given the opportunity to receive study treatment until the end of study treatment period as defined in [Section 6.1](#).

During the treatment phase, the patients will receive either asciminib treatment 40 mg BID, 80 mg QD or 200 mg (if T315I Mutation).

The dose can be modified, if required from the perspective of tolerance, following the guidance in [Section 6.5](#). Treatment will be administered until patient experiences treatment failure, unacceptable toxicity, disease progression, death, lost to follow-up and/or treatment is discontinued at the discretion of the investigator or withdrawal of consent.

The patients are advised to adhere to the food restrictions during the treatment (fasting status regarding study treatment administration, avoidance of prohibited concomitant medication).

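### Protocol Section 6.5 forbids the dose holds that its own subsections require, and the 28-day banner of Table 6-2 conflicts with the 42-day cytopenia limit

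*Protocol*

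**What the plan says.** Section 6.5 of the protocol, the parent section for dose escalation and modification, states: "Investigational or other study treatment dose adjustments and/or interruptions are not permitted". It names no exception.

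Other sections require or advise what that sentence rules out:

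- Section 6.5.2 introduces holds and reductions, some recommended and some mandatory. It says that departures from the mandatory ones "are not allowed and mandatory interruptions or reductions must be strictly followed". Table 6-2 lists them and Table 6-3 gives a reduced dose for each cohort.
- Section 6.5.2.1, for confirmed QTcF prolongation: "Interrupt study treatment until confirmed resolution of QTcF and as per dose reduction guidelines for non-hematological AEs".
- Section 6.2.2, Cohort C, when a strong CYP3A inhibitor cannot be avoided and "cannot be switched to an alternative therapy that does not strongly inhibit CYP3A, asciminib must be interrupted".
- Section 6.2.2, when a drug with a known risk of Torsades de Pointes "is required and cannot be avoided, study drug must be interrupted".
- Section 6.6.3, advisory: patients with COVID-19 "should be placed immediately on treatment break or delay while a determination is made about the next steps".

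Two further sections assume that modification is allowed. Section 8.1.3 says "The dose can be modified, if required from the perspective of tolerance, following the guidance in" Section 6.5. Section 4.4 counts "adherence to dose modification and interruption guidance provided in the protocol" among the measures that limit risk.

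On the length of a hold, the Table 6-2 banner requires discontinuation when an interruption passes 28 days, whatever the toxicity. The text of Section 6.5.2 confines that limit to non-hematologic toxicity. That text and the table's hematologic header both give a separate limit for Grade 3 or 4 cytopenia: discontinue if it lasts beyond 42 days without recovering to Grade 2.

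Section 6.5.2 permits one re-escalation per patient and names 40 mg BID as the only target. The Table 6-2 row on recurrent cytopenias tells sites to reduce imatinib as well as asciminib.

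**The concern.** These are instructions that sites act on. Section 8.1.3 sends the investigator to Section 6.5 for dose-modification guidance, and the first sentence there forbids modification. Read literally, every hold that Section 6.5.2 mandates is a departure from Section 6.5.

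The banner matters in a different way. A site working from the table alone would take a patient with slow-recovering neutropenia or thrombocytopenia off study after 28 days of interruption, although the cytopenia rule sets its limit at 42. Sites that follow different lines would discontinue different patients. Discontinuations of this kind are reported: AEs leading to treatment discontinuation are tabulated (Protocol 12.7.2, SAP 2.6.1), and a patient who stops before responding counts as a non-responder (SAP 2.8.2).

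**Working it through.** The plan has no figure of its own to reproduce on this point. The check compares texts, with simple arithmetic for the overlap of the two limits and for daily doses.

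**Step 1. Can the Section 6.5 sentence be read narrowly?** One might take it to concern escalation only. It cannot: escalation has its own rule in Section 6.5.1, and the Section 6.5 sentence names interruptions. It therefore contradicts Sections 6.5.2, 6.5.2.1 and 6.2.2, which are mandatory, and is at odds with Section 6.6.3, which is advisory.

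**Step 2. Which side is wrong?** Section 6.1.5 points to Section 6.5.2 for continuation of treatment. Sections 4.4 and 8.1.3 rely on modification guidance. SAP 2.4.1 summarises reductions and interruptions with their reasons. All of these agree with Section 6.5.2. The Section 6.5 sentence is the outlier.

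**Step 3. The 28-day and 42-day limits.** The clocks differ. The banner counts days of interruption; the cytopenia rule counts days of toxicity. Table 6-2 holds the drug in Grade 3 or 4 neutropenia and thrombocytopenia until recovery to Grade 2 or better, so the two clocks run together once the hold begins. Let *d* be the day of interruption and *k* the number of days from onset of the cytopenia to the start of the hold. The rules disagree when

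- *d* ≥ 29 (banner triggered), and
- *d* + *k* ≤ 42 (cytopenia limit not yet passed).

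The number of conflicting days is (42 − *k*) − 29 + 1 = 14 − *k*, and zero once *k* reaches 14.

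| Days from onset to hold (*k*) | Conflicting interruption days | Number |
|---|---|---|
| 0 | 29 to 42 | 14 |
| 7 | 29 to 35 | 7 |
| 14 or more | none | 0 |

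The documents do not give *k*, so it is an assumption. The same algebra shows that under the banner as printed the 42-day limit would come first only if the hold began more than 14 days after onset. In all other cases the banner would make it redundant.

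**Step 4. Re-escalation to 40 mg BID (80 mg/day), applied literally to the reduced doses in Table 6-3.**

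- Cohort A: 20 mg BID = 40 mg/day, returning to 80 mg/day on the assigned schedule. This works.
- Cohort B: 40 mg QD = 40 mg/day, returning to 80 mg/day but on Cohort A's twice-daily schedule.
- Cohort C: 200 mg QD = 200 mg/day, going to 80 mg/day, which is a decrease.

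The sentence fits Cohort A only. Section 6.5.1 bars going above the starting dose and does not mention returning to it.

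**The case against.** The best defence is that the intent is plain. A detailed, binding subsection overrides one stray lead-in sentence. Reduction steps exist for every cohort, the case report form has fields for reductions and interruptions, and Section 14.1 expects investigators to take immediate safety action even when it deviates from the protocol. This stands as an argument about consequences. A reader might infer from Section 6.5 that sites will withhold mandated holds and that patients will be harmed; the surrounding text makes that unlikely. It does not make the sentence correct, and Section 14.1 treats such action as a possible deviation to be notified, not as a replacement for a sound rule.

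On the two limits, the defence is that both are triggers for discontinuation: the 42-day rule never says that treatment must continue to day 42. That is right, and a reader should not see two opposite commands there. A site could satisfy both by stopping after 28 days. The inconsistency is that doing so discontinues patients whom the cytopenia rows would still hold and then restart one dose level lower, and whom the Section 6.5.2 text exempts from the 28-day limit. That text, just above the table, shows that the banner lacks a qualifier.

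On re-escalation, the literal reading is that only a return to 40 mg BID is authorised, so nothing is missing. Against that, the once-per-patient limit is worded for any patient and could suggest a wider intent. The documents do not settle it.

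**Conclusion.** The point holds as an internal inconsistency of moderate severity; no design choice is at issue. Section 6.5 is wrong as written, and the Table 6-2 banner lacks the word that would reconcile it with the Section 6.5.2 text and the hematologic header. The banner conflict spans at most 14 interruption days (29 to 42), on the assumption that the hold starts at onset, and shrinks day for day with any delay.

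Three wider readings are not supported. Counting every table row that the Section 6.5 sentence contradicts, or every page on which the banner is reprinted, does not measure patients at risk: there is one wrong sentence and one wrong banner. The 70 planned patients in Cohorts B and C (45 + 25, of 115) are not the number without a re-escalation rule. Only those who are dose-reduced could need one, and the documents give no reduction rate for this study. Finally, nothing here changes the sample size or any analysis method.

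The scope of re-escalation and the mention of imatinib are minor clarifications.

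**What to change.** 1. In Section 6.5, keep the prohibition and add an exception clause: *except as specified in Sections 6.2.2, 6.5.2, 6.5.2.1 and 6.6.3*.
2. In the Table 6-2 banner, wherever it is printed, insert *non-hematologic* before *toxicity*, to match the Section 6.5.2 text.
3. Minor: state whether re-escalation applies to Cohort A only or also allows Cohorts B and C to return to their assigned starting dose. Extending it is a medical decision for the sponsor, since Section 4.2 reports more discontinuations due to AEs, dose-limiting toxicities and Grade 3/4 events as the dose rises.
4. Clerical: delete the mention of imatinib in the recurrent-cytopenia row, since this is a monotherapy study.

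The cost is a few words in one protocol amendment or clarification. Only a decision to widen re-escalation would need medical review. Design, sample size and SAP stay as they are.
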